2.2. Objectives

The primary objective of the trial is to evaluate the effectiveness of gabapentin to decrease pain and irritability in children with SNI, when the source of pain and irritability is attributed to neurological dysregulation (nociplastic pain), as measured by parent reported pain scores. This objective corresponds to the primary outcome listed in section 3.4.1.

We will compare the gabapentin versus placebo along an escalating dose range for both individual subjects and for the group. We will aggregate the results of the completed N-of-1 trials across all subjects to estimate the group level comparative effectiveness of gabapentin in reducing pain and irritability.

The secondary objectives are to:

- 1. Identify the optimal dosing of gabapentin in reducing pain and irritability (Corresponds to secondary outcomes 3.4.2 and 3.4.3).
- 2. Identify the latency time for gabapentin to show effectiveness (Corresponds to secondary outcome 3.4.4).
- 3. Evaluate the safety and tolerability of gabapentin (Corresponds to secondary outcome 3.4.5).
- 4. An Exploratory objective will be to evaluate whether parent/caregiver stress and function improve if gabapentin reduces children's pain and irritability. This objective corresponds to the Exploratory outcome listed in section 3.4.6.

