3.6. Sample size

We will enroll 10 participants in the gabapentin trial. In personalized trials, sample size refers to the number of assessments for each patient. As we had no prior data from which to estimate within patient day-to-day variability in pain scores nor an expected effect size for symptom reduction when comparing gabapentin to placebo in this population, we did not calculate statistical power a priori for the number of assessments per treatment period. Rather, the sample size for each personalized trial was based on collecting the maximal amount of data expected to be tolerable from the perspective of patient study burden. Ten participants is a sampling number based on current recruitment into the PIUO Study (REB #H16-03288) from which we expect to draw the majority of participants for this trial. This number, with the repeated measures obtained throughout the treatment periods should provide sufficient data to address the study goals.

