Missed visits

If a participant misses a scheduled study visit or contact with prior permission, the researchers will try to contact him/her and schedule a visit as soon as possible. Participants who stop taking the study medication for any reason will be asked to complete the Final Study Visit.

Withdrawal from trial

A participant may be withdrawn from the trial due to the following reasons including, but not limited to:

- Participant's request
- Severe Adverse Events (SAE) and/or other safety reasons
- A new health condition appears that is suspected to require care or medications prohibited by the protocol

• It is in the participant's best interest according to the Investigator's clinical judgment

Participants are free to withdraw from the study at any time and for whatever reason, specified or unspecified, and without prejudice to his or her medical care by a physician.

All premature discontinuations and their causes must be documented by the Investigator on the appropriate CRF pages. The reason for, and date of, the discontinuation, and the date of the last dose of the study medication, must be recorded in the appropriate section of the CRF. While the treatment with the investigational product will discontinue if a participant withdraws from the trial, participants not completing the entire study should be fully evaluated (i.e., last study contact and follow up procedures performed), wherever possible.

Withdrawn participants will be replaced via ongoing recruitment in order to meet the goal of obtaining data from 10 participants completing the trial.

Early termination visit

If a participant withdraws or is removed from the trial for any reason prior to the completion of the trial, the reason for, and date of, the discontinuation, and date of the last dose of study drug, must be recorded in the appropriate section of the Case Report Form (CRF).

At the time of discontinuation, every effort should be made to ensure that: (1) Procedures and evaluations scheduled for the End of Study are performed, including the assessment of AEs. (2) Study drugs are returned and inventoried. (3) Study staff make an appointment for a safety follow-up visit if required.

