3.10. Statistical Methods

All data will be entered into a REDCap database, either directly from participants using a web-based entry system, or for those using paper, transferred from data collection sheets by a research assistant. The study cohort will be described in tables with descriptive statistics (mean, median and standard deviation) where appropriate. The primary method of analyzing the data was by systematic visual graphing of the pain scale over the exposure/placebo conditions. This is the method recommended by the CONSORT collaboration, extension for N-of-1 studies (CENT).⁵⁸

Data analysis for the primary outcome will be conducted within each N-of-1 trial and will also be aggregated across trials using measurements taken on days 11-19.

For each individual, the pain and irritability score on the NCCPC-R will be calculated over days 11-19 for both the treatment and control periods. These means will then be compared statistically using a Bayesian model, reporting the posterior mean difference using a non-informative prior for the means and variance. The posterior probability that the mean of the treatment is greater than the mean of the control will also be reported. Because of the use of non-informative priors, this analysis is very similar to a t-test.

We will also aggregate the means across participants using Bayesian linear mixed models in order to compare the average effect of the treatment as well as obtain better estimates of each individual's effect through borrowing of strength from others' data.

Additional analyses

Secondary outcomes will be assessed as follows:

- For each patient who benefits from gabapentin, the lowest dose that was effective in reducing pain scores will be calculated as the lowest dose that gives at least an 11 point reduction with no rebound over 3 days in the NCCPC-R score compared to baseline during day 11-19 on active drug. The set of lowest doses will be summarized descriptively.
- For each patient who benefits from gabapentin, the maximal effect dose will be calculated as the dose that gives the largest improvement in the NCPCC-R score compared to baseline during days 11-19 on active drug. The set of lowest doses will be summarized descriptively.

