- The latency time in days to the onset of maximum relief of pain and irritability as measured by the NCCPC-R score will be the day that gives the largest improvement in the NCPCC-R score compared to baseline during days 0-19 on active drug. The set of latency times will be summarized descriptively.
- Adverse Events will be compared between treatment arms descriptively.
- PROMIS-57 scores reported by parent/caregiver will be computed for each patient on each arm by averaging the scores taken on days 12, 16 and 19 and comparing these mean scores. The differences in mean scores between the treatment and placebo arms will be summarized descriptively.

Analysis population and missing data

For the primary outcome, any missing days will be excluded from calculation of the mean.

For secondary outcomes, missing values will be disregarded in the sense that only observed values will be used to compute the lowest dose, maximal effect dose, latency time and PROMIS-57 mean scores.

Analyses will use the intent-to-treat principle meaning that observations in a period will be ascribed to the treatment to which that period was randomized.

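### Replacing withdrawn children until 10 complete, and aggregating completed trials, makes the group efficacy estimate a completer estimate as written

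*Protocol*

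**What the plan says.** Five parts of the protocol bear on who enters the group efficacy estimate.

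- **Section 3.8, Withdrawal from trial:** "Withdrawn participants will be replaced via ongoing recruitment in order to meet the goal of obtaining data from 10 participants completing the trial". The listed grounds for withdrawal include "Severe Adverse Events (SAE) and/or other safety reasons".
- **Section 3.8, Missed visits:** "Participants who stop taking the study medication for any reason will be asked to complete the Final Study Visit". Continued scoring on days 11-19 after stopping is not mentioned.
- **Section 2.2, Objectives:** "We will aggregate the results of the completed N-of-1 trials across all subjects", in order to estimate the group-level effect.
- **Section 3.10, Statistical Methods:** "We will also aggregate the means across participants using Bayesian linear mixed models". Under the analysis-population heading it adds: "Analyses will use the intent-to-treat principle meaning that observations in a period will be ascribed to the treatment to which that period was randomized". The rule for gaps is "For the primary outcome, any missing days will be excluded from calculation of the mean".
- **Section 3.6, Sample size:** "We will enroll 10 participants in the gabapentin trial".

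**The concern.** Section 2.2 is the only place that says which individual trials feed the group effect, and it names the completed ones. Section 3.8 sets recruitment to match, by adding children until 10 have finished. Followed literally, a child who withdraws is replaced in the count and drops out of the group estimate.

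The intent-to-treat label in section 3.10 does not prevent this. Its definition concerns the treatment to which a period's observations are attributed. It does not say that every randomised child is analysed, although a reader will usually take the label to mean that.

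Withdrawal may also depend on treatment. Safety is a listed ground. Section 3.12 allows the Medical Monitor, once told which preparation was in use, to advise on withdrawal, so some withdrawals can be decided with knowledge of the arm. If children who leave differ in benefit from those who stay, the completer mean is not the mean for the children randomised. With a target of 10, and with section 2.1 saying that the results should inform a much larger trial, a few uncounted children matter.

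**Working it through.** **1. No figure to reproduce.** The number 10 in section 3.6 rests on feasibility. No power, effect size, standard deviation or dropout rate is given. The check is therefore a reading of the sections, followed by illustrations on stated assumptions.

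**2. What each rule does with a withdrawn child.** Table 4 schedules the NCCPC-R on each of days 11-19, which is 9 scores per period and 18 over both. Table 3 puts study end at day 26 of the second period.

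| Child leaves | Day 11-19 scores | Completed trials aggregated | All randomised with any day 11-19 score |
|---|---|---|---|
| Before day 11 of period 1 | none | out | out |
| From day 11 of period 1 to before day 11 of period 2 | period 1 only, up to 9 | out | in, but adds little to the within-child contrast |
| During days 11-19 of period 2 | both periods, second one partial | out | in, with a contrast |
| After day 19 of period 2, before study end | up to all 18 | out, if completion means reaching study end | in, with a full contrast |

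The two rules differ in the last three rows. In the last two, usable primary-outcome data would be set aside.

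**3. How often replacement would be needed.** Assume each child withdraws independently with probability d; the protocol gives no value. The number to randomise is 10/(1 - d), rounded up. The chance that the first 10 all complete is (1 - d)^10.

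| d | 10/(1 - d) | Randomised | Outside a completer analysis | (1 - d)^10 |
|---|---|---|---|---|
| 0.10 | 11.1 | 12 | 2 | 0.35 |
| 0.20 | 12.5 | 13 | 3 | 0.11 |
| 0.30 | 14.3 | 15 | 5 | 0.03 |

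On these assumptions replacement would probably be used, and the enrolment figure in section 3.6 would probably be exceeded.

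**4. Possible gap between completers and all randomised.** This is an illustration only. Assume that true effects vary between children normally with standard deviation (SD) 5 or 10 NCCPC-R points. Let the log-odds of withdrawal rise by s for each SD less benefit, with overall withdrawal at 10% to 30%. In a simulation of 2,000,000 children per setting, completer mean minus all-randomised mean was:

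| s | SD 5 | SD 10 |
|---|---|---|
| 0 | 0 | 0 |
| 0.5 | 0.25 to 0.72 | 0.49 to 1.43 |
| 1.0 | 0.45 to 1.27 | 0.90 to 2.53 |

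The result was the same, to rounding, for a mean effect of 0 or 5 points. If withdrawal were instead likelier in children with more benefit, the model is symmetric and the signs reverse. For scale, section 3.4 takes 11 points as the meaningful change. These figures compare completers with all children randomised. They do not measure what the fix would recover, because a child with no day 11-19 score stays out under either rule.

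**The case against.** The best defence is that section 3.10, the analysis section, contains no completer restriction. Its mixed model is described across participants, and its missing-data rule drops days, not children. The word completed in section 2.2 could mean only that pooling waits until the individual trials are over. Section 3.8 sets a recruitment target and does not order a withdrawn child's data to be discarded. Replacement on its own causes no bias, and details of the analysis set are often left to a SAP.

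Much of this stands. That only completers are aggregated is a reading of section 2.2, and section 3.10 would allow partial data. Nor does it literally contradict the intent-to-treat sentence, which is defined narrowly. What remains is that the one sentence naming the trials to be aggregated names completed ones, and the recruitment rule matches it. That is a stated rule, not a detail left open.

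A reader might infer that the adverse event burden is understated. The protocol does not support that. Section 3.12 keeps all data in the safety analyses, with no exclusions for protocol deviations, and records events up to departure, including early discontinuation.

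A reader might also infer that benefit is necessarily inflated. Section 3.8 lists several grounds for withdrawal, and lack of effect is not among them. The titration adjustments in sections 3.12 and 4.2, mirrored in both periods, may reduce withdrawals for tolerability. Children could also leave during placebo because pain persists; if some of them would have responded to gabapentin, losing them would bias the estimate downwards.

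**Conclusion.** The point holds for efficacy. As written, sections 2.2 and 3.8 together give a completer estimate of the group effect, under an intent-to-treat label in section 3.10 that does not say who is analysed. Because withdrawal can be for safety reasons, the estimate may be biased. Size and direction cannot be derived from the protocol. Under the assumptions shown, the gap is nil if withdrawal is unrelated to effect. It is about 0.25 to 2.5 points if children with less benefit are likelier to leave, and of opposite sign if the dependence runs the other way.

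A reader might credit completers with 11 points and withdrawn children with none, and read off a percentage inflation. The documents do not support such a figure. The 11 points are a threshold for meaningful change, not an expected group effect. Nothing says that withdrawn children gain nothing. A child without day 11-19 scores would remain outside the repaired analysis as well.

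Separately, 10 enrolled (section 3.6) and 10 completing (section 3.8) cannot both hold once any child withdraws. The change should be made; it is a matter of definition and leaves the design as it is.

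**What to change.** 1. In section 2.2, base the group estimate on all randomised children instead of completed trials.
2. In section 3.10, state that the aggregate mixed model includes every randomised child with at least one NCCPC-R score on days 11-19 of either period, whether or not that child was replaced. Give the completer result as a sensitivity analysis.
3. Commit to reporting the numbers randomised, withdrawn (by period and reason) and replaced. This is needed because children who leave before day 11 of the first period add nothing to the contrast, and those with one period add little, so the model alone cannot show the extent of the loss. Section 3.8 already requires the reason and dates of each discontinuation to be recorded.
4. Align sections 3.6 and 3.8 on whether 10 is the number enrolled or the number completing.

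The cost is a few sentences and one additional model run. No visit, dose or clinical rule changes. The estimate may move in either direction.

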3.9. Data Management

Data Collection

Data will be collected on CRFs during screening and at all the study visits/contacts. Data from source documents will entered and validated in a REDCap database for which special privacy and security measures are in place. All data entered into REDCap will be de-identified and collected data will only be viewed by study team members granted specific rights. However, as surveys will be sent via e-mail to participants, e-mail addresses will be collected and linked to the participant study ID within REDCap in order to facilitate data collection. REDCap has the capacity to store 'live' data for multiple, ongoing study databases simultaneously where each individual study database has the option of supporting multiple centers. The REDCap database will be provided by the CHILD-BRIGHT Data Coordinating Centre (DCC) which is managed by the Women & Children's Health Research Institute at the University of Alberta. The database itself is housed on secure servers hosted in a secure data Centre in the basement of the University of Alberta Hospital behind the MEDIT firewall. The REDCap database will be annulled and the electronic data deleted 5 years after the study has been completed.

Detailed aspects of data handling will be laid out in the Data Management Plan.

Source Documents

The Investigator must maintain adequate and accurate source documents upon which CRFs for each participant are based. They are to be separate and distinct from CRFs except for cases in which the Sponsor has pre-determined that direct data entry into specified pages of the participant's CRF is appropriate. These records should include detailed notes on:

- Oral and written communication with participant and caregiver regarding the study treatment (risks/benefits)
- Participation in trial and signed and dated informed consent forms
- Inclusion and exclusion criteria details
- Visit dates
- Adverse events and concomitant medication
- Results of relevant examinations
- Participant's exposure to any concomitant therapy (start/stop dates, dosing details)
- Reason for premature discontinuation (if applicable)
- Enrollment number
- Compliance/noncompliance protocol deviation information

Record Retention

The Investigator will maintain all study records according to the ICH-GCP and applicable regulatory requirement(s). Records will be retained for 25 years, in accordance with applicable regulatory requirement(s). If the Investigator withdraws from the responsibility of keeping the study records, custody must be transferred to a person willing to accept the responsibility and the Sponsor-Investigator notified. The Investigator should ensure that no destruction of medical records occurs without the written approval of the Sponsor-Investigator. Data kept within the REDCap database will be deleted only upon request by the Sponsor, in accordance with this protocol

3.10. Statistical Methods

All data will be entered into a REDCap database, either directly from participants using a web-based entry system, or for those using paper, transferred from data collection sheets by a research assistant. The study cohort will be described in tables with descriptive statistics (mean, median and standard deviation) where appropriate. The primary method of analyzing the data was by systematic visual graphing of the pain scale over the exposure/placebo conditions. This is the method recommended by the CONSORT collaboration, extension for N-of-1 studies (CENT).⁵⁸

Data analysis for the primary outcome will be conducted within each N-of-1 trial and will also be aggregated across trials using measurements taken on days 11-19.

For each individual, the pain and irritability score on the NCCPC-R will be calculated over days 11-19 for both the treatment and control periods. These means will then be compared statistically using a Bayesian model, reporting the posterior mean difference using a non-informative prior for the means and variance. The posterior probability that the mean of the treatment is greater than the mean of the control will also be reported. Because of the use of non-informative priors, this analysis is very similar to a t-test.

We will also aggregate the means across participants using Bayesian linear mixed models in order to compare the average effect of the treatment as well as obtain better estimates of each individual's effect through borrowing of strength from others' data.

Additional analyses

Secondary outcomes will be assessed as follows:

- For each patient who benefits from gabapentin, the lowest dose that was effective in reducing pain scores will be calculated as the lowest dose that gives at least an 11 point reduction with no rebound over 3 days in the NCCPC-R score compared to baseline during day 11-19 on active drug. The set of lowest doses will be summarized descriptively.
- For each patient who benefits from gabapentin, the maximal effect dose will be calculated as the dose that gives the largest improvement in the NCPCC-R score compared to baseline during days 11-19 on active drug. The set of lowest doses will be summarized descriptively.
- The latency time in days to the onset of maximum relief of pain and irritability as measured by the NCCPC-R score will be the day that gives the largest improvement in the NCPCC-R score compared to baseline during days 0-19 on active drug. The set of latency times will be summarized descriptively.
- Adverse Events will be compared between treatment arms descriptively.
- PROMIS-57 scores reported by parent/caregiver will be computed for each patient on each arm by averaging the scores taken on days 12, 16 and 19 and comparing these mean scores. The differences in mean scores between the treatment and placebo arms will be summarized descriptively.

Analysis population and missing data

For the primary outcome, any missing days will be excluded from calculation of the mean.

For secondary outcomes, missing values will be disregarded in the sense that only observed values will be used to compute the lowest dose, maximal effect dose, latency time and PROMIS-57 mean scores.

Analyses will use the intent-to-treat principle meaning that observations in a period will be ascribed to the treatment to which that period was randomized.

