3.4. Outcomes

1. Primary Outcome: The mean pain and irritability score on the NCCPC-R through days 11-19 on active drug compared to placebo.

[figure not shown]
An 11-point decrement in the NCCPC-R score with no rebound x 3 days is considered clinically meaningful minimum change (improvement).

Secondary Outcomes:

- 2. For patients who benefited from gabapentin, identification of the lowest dose that was effective in reducing pain scores, as shown by a improvement the NCCPC-R score compared to baseline during day 11-19 on active drug.
- 3. For patients who benefited from gabapentin, identification of the maximal effect dosage as measured by the largest improvement in the NCPCC-R score compared to baseline during days 11-19 on active drug.
- 4. Identification of the latency time in days to the onset of maximum relief of pain and irritability as measured by the NCCPC-R score over days 0-19.
- 5. Adverse Events Collection demonstrates the AE on treatment arm do not exceed the frequency found in the Product Monograph for children receiving gabapentin.
- 6. Exploratory Outcome: PROMIS-57 scores reported by parent/caregiver are improved on the treatment arm compared to the placebo arm.

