Randomization will be undertaken by the study pharmacist, using a computer-generated randomization. Before the 2 periods (pair of active drug (G) or placebo (P)) the pharmacist will generate a random code indicating whether G or P is to be given first. The randomization table will be kept in the Research Pharmacy office, which has restricted access. In case of a serious adverse event and when necessary, the randomization of any one participant can be unmasked to the Principal Investigator. This will be done through direct contact between the pharmacist and the Principal Investigator.

Study Contacts

Contact with study participants during the trial will consist of online surveys and telephone check ins. Contacts will be scheduled to overlap with changes in dose. Each contact will last approximately 10 minutes. The following study tools will be used at study contacts (see table 4 for a schedule of assessments at the time of study contacts):

- Health Update (Appendix 6) (midway through each sequence and at study end)
- Pain Survey (Appendix) (only on the first or last day of each block, not both)
- NCCPC-R (Appendix 7)
- PROMIS-57 (Appendix 8)
- Adverse Events Log (Appendix 10)
- Concomitant Medications (Appendix 11)

When the participant begins Sequence 2, the drug will be dispensed again in person.

Follow up

Two weeks past Study End the randomization sequence for individual participants will be unblinded and shared with the participants along with their individual results. The results will be presented numerically and graphically. Graphs showing the outcomes over time on the medication and placebo arms, summarizing the dosage used at individual outcome points will be provided. This will allow participants to make decisions regarding continuing gabapentin (in consultation with their primary caregiver) and is in keeping the Strategies for Patient Oriented Research (SPOR) principles that this clinical care trial is based on. At this time, the participant's caregiver will also be given the opportunity to provide feedback to the research team via the Participation Questionnaire (Appendix 9).

For any participant that experiences a SAE, there will be an initial contact at the time of the event and appropriate evaluation undertaken by the physician investigator. Another safety follow-up visit will be scheduled within 7 days following the final study visit to review the event. Additional follow-up may be done based on the investigator's medical judgment.

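### The per-child posterior probability in Protocol 3.10 points the wrong way: on a pain score, a greater mean on treatment means gabapentin did worse than placebo

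*Protocol*

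**What the plan says.** Section 3.10 describes the within-child analysis of the primary outcome. For each individual, "the pain and irritability score on the NCCPC-R will be calculated over days 11-19 for both the treatment and control periods". The period means are then compared in a Bayesian model with non-informative priors for the means and variance, and the posterior mean difference is reported. The next sentence reads: "The posterior probability that the mean of the treatment is greater than the mean of the control will also be reported". The model is characterised as follows: "Because of the use of non-informative priors, this analysis is very similar to a t-test".

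Two other sections fix the direction of the scale. Section 2.2: "The primary objective of the trial is to evaluate the effectiveness of gabapentin to decrease pain and irritability in children with SNI". Section 3.4: "An 11-point decrement in the NCCPC-R score with no rebound x 3 days is considered clinically meaningful minimum change (improvement".

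The results also go back to families. Under Follow up in section 3.8, each child's sequence is to be "unblinded and shared with the participants along with their individual results. The results will be presented numerically and graphically", so that families can decide whether to continue gabapentin.

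**The concern.** The means being compared are means of the pain score itself, so a greater mean on treatment is more pain on gabapentin. A reader who meets a posterior probability in the effectiveness analysis of a primary outcome will normally take a value near 1 as evidence for the drug. Here it is evidence against it: the number falls towards 0 for a child who improves and rises towards 1 for a child who gets worse.

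This is the only posterior probability the protocol states for the primary outcome. The sign convention of the accompanying posterior mean difference is not given either, so that figure does not by itself correct a misreading. The sentence could be programmed as written and carried into a report. The protocol does not say that this probability is among the numbers given to families. If it is, a low value for a child who improved could be read as a sign that the drug did not help.

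**Working it through.** **Step 1: what is compared.** In 3.10 the means entering the model are the period means of the NCCPC-R score over days 11-19. Section 3.4 agrees: the primary outcome is the mean score on active drug compared with placebo. Neither place defines the compared quantity as a change from baseline or an improvement.

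**Step 2: which direction is good.** Section 2.2 aims for a decrease in pain. Section 3.4 calls an 11-point decrement an improvement. Later in 3.10 itself, an effective dose is defined by a reduction of at least 11 points. No section reverses the score.

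**Step 3: direction of the probability.** Let d be the observed difference in means, gabapentin minus placebo. With non-informative priors, the posterior of the true difference is symmetric about d. Under a common variance it is a scaled t distribution, so

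P(treatment mean > control mean) = F(d / se), with se = SD × √(2/n) and df = 2n − 2,

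where F is the t distribution function and n is the number of scored days per period. F is below 0.5 whenever d is negative (less pain on gabapentin), equals 0.5 at d = 0, and is above 0.5 whenever d is positive. This holds for any SD and any n.

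**Step 4: illustration.** The protocol has no figure of its own to reproduce. Inputs:
- d = −11, the meaningful change in 3.4.
- n = 9, because Table 4 schedules the NCCPC-R on each of days 11 to 19. Also n = 6, an assumed case with three missing days, since 3.10 says: "For the primary outcome, any missing days will be excluded from calculation of the mean".
- SD = 8, 10 or 15, assumed, because section 3.6 states: "As we had no prior data from which to estimate within patient day-to-day variability in pain scores".
- Independent scores and equal variances, assumed.

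Worked case, n = 9 and SD = 10: se = 10 × √(2/9) = 4.714; 11 / 4.714 = 2.333; on 16 df the reported value is 0.0165 and its complement 0.9835. A simulation of the posterior gave 0.0167.

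| n per period | df | SD (assumed) | 11/se | Reported as written | Probability of benefit |
|---|---|---|---|---|---|
| 9 | 16 | 8 | 2.917 | 0.005 | 0.995 |
| 9 | 16 | 10 | 2.333 | 0.016 | 0.984 |
| 9 | 16 | 15 | 1.556 | 0.070 | 0.930 |
| 6 | 10 | 8 | 2.382 | 0.019 | 0.981 |
| 6 | 10 | 10 | 1.905 | 0.043 | 0.957 |
| 6 | 10 | 15 | 1.270 | 0.116 | 0.884 |

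For a child whose mean is 11 points higher on gabapentin, the last two columns change places. With n = 9 and SD 10, that child would be reported at 0.984.

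**The case against.** The strongest reply is that the sentence is not false. It never calls the quantity a probability of benefit. It names a well-defined posterior probability, and for a continuous posterior the probability of benefit is one minus it. Nothing depends on it: no success threshold, responder definition, stopping rule or dose rule uses it, and the aggregate analysis is a separate mixed model for which no posterior probability is stated. Visual graphing is named as the primary method, the posterior mean difference is reported alongside, and families receive graphs on which lower scores during gabapentin would be plain. The route to misleading a family is conjecture, because the protocol does not say the probability is shared. Finally, the numerical illustration only pairs p with 1 − p, and its independence assumption is doubtful for daily scores on one child while doses step up within the window.

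Most of this stands, and it limits the weight of the point. It does not make the sentence right. The only reading that would make the sentence a probability of benefit is that the means are mean improvements, and 3.10 rules that out because they are means of the score. Nor is the quantity labelled as a probability of harm; it sits unlabelled in the effectiveness analysis. The objection to the illustration is fair as to the exact values, but the direction needs none of them.

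**Conclusion.** The point holds. As written, the per-child probability is the probability that gabapentin is worse than placebo, which is the reverse of what the primary objective asks. The conclusion about direction rests on the text alone and on the symmetry of the posterior under non-informative priors. The tabulated values also rest on assumed SDs, independence and equal variances, and only show how far apart the two readings lie.

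It should be fixed, but its reach is small. It affects one reported number per child and no estimate or decision rule, and the harm is confined to misinterpretation. This is not a matter to leave to a statistical analysis plan, because the protocol does not leave the direction open: it states one.

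**What to change.** In section 3.10, replace the sentence with:

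> The posterior probability that the mean NCCPC-R score on gabapentin is lower than on placebo will also be reported.

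It would help to state in the same place that the posterior mean difference is gabapentin minus placebo, so that a negative value means benefit. If the existing direction is kept, it should be labelled as the probability of a worse score on gabapentin.

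The cost is one word (greater to lower) or one sentence. Data collection, model, priors, estimates and sample size are unchanged.
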